5.0 PATIENT EVALUATION FLOWSHEET: PRE-TREATMENT, ON STUDY, AND AFTER TREATMENT

All patients entered on study must be evaluated according to the schedule outlined below with documentation submitted according to the schedule in Appendix II.

Required Investigations	Prior To Enrollment		During Protocol Treatment Prior to each FOLFOX or CAPOX cycle	Pre-Excision 2 weeks (FOLFOX) or 3 weeks (CAPOX) after last injection in last cycle of chemotherapy	Excision within 3 weeks after pre-excision visit	After Excision ¹		First Disease Relapse ²	After First Disease Relapse (Phone Contacts Acceptable) ³
	Within 90 days	Within 30 days				30 d	Months 6, 12, 18, 24, 30 and 36.		
History and Physical Exam									
Including: height (baseline only), weight, ECOG performance status		X	X ⁴	X		X	X		
Concomitant Medications		X	X ⁴	X	X	X			
Hematology									
CBC, differential (including lymphocytes), platelets		X	X ⁴	X					
Coagulation									
PTT, PT/INR		X		X					
Biochemistry									
ALT, serum creatinine, total bilirubin		X	X ⁴	X					
Creatinine Clearance (calculated)		X	X ⁴	X					
Serum CEA		X		X			X		
Correlative Studies									
Tumour tissue specimen banking ⁵	X				X				
Whole blood (for ctDNA), whole blood, serum and plasma ^{5, 6}		X		X		12, 24 and 36 ⁷		X ^{7, 8}	
Radiology									
MRI pelvis	X			X		6, 18 and 30 ⁷		X	
CT pelvis ⁹ (optional if pelvic MRI performed)	X					12, 24 and 36		X	
CT chest ⁹	X					12, 24 and 36		X	
CT abdomen with contrast ¹⁰	X					12, 24 and 36		X	
Sigmoidoscopy/Colonoscopy ¹¹	X			X		X ¹²		X	
Other Investigations									
Biopsy confirming invasive well-moderately differentiated rectal adenocarcinoma	X ¹³				X			X ¹⁴	
Pregnancy test ¹³		X							
Submission of tumour tissue for retrospective central yp staging confirmation (mandatory)					X				
Capecitabine patient diary			Daily ¹⁶						
Adverse Events									
Adverse event assessment ¹⁷		X	X	X	X	X	X ¹⁸	X ¹⁸	X ¹⁸

table continues on next page

Required Investigations	Prior To Enrollment		During Protocol Treatment Prior to each FOLFOX or CAPOX cycle	Pre-Excision 2 weeks (FOLFOX) or 3 weeks (CAPOX) after last injection in last cycle of chemotherapy	Excision within 3 weeks after pre-excision visit	After Excision ¹		First Disease Relapse ²	After First Disease Relapse (Phone Contacts Acceptable) ³
	Within 90 days	Within 30 days				30 d	Months 6, 12, 18, 24, 30 and 36		
Quality of Life									
EORTC QLQ-30 and EORTC QLQ-CR29		X		X			6, 12, 24 and 36		

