LARS and the Fecal Incontinence Quality of Life Instrument		X		X			6, 12, 24 and 36		
Health Economics									
EQ-5D-5L		X	X ¹⁹	X		X	6, 12, 24 and 36		
Phone Contact									
Survival information								X	X
1. Timing for visits after excision are scheduled from last tumour excision date: a. For patients having TME as first protocol excision: from TME date b. For patients having TEMS/TAMIS as first protocol excision: from TEMS/TAMIS date c. For patients having TEMS/TAMIS as first protocol excision and then having a TME: from TME date 2. See protocol section 8 for definitions. 3. Phone contacts or visits after first disease relapse are required every 6 months from date of relapse. 4. Tests may be done on the date of treatment or, if not possible, the previous working day before treatment day. If treatment is to begin on a Monday, may be done on the previous Friday (maximum 72 hours prior to treatment). 5. Please also see protocol Section 12.0 and details for collection, processing, storing, and shipping these samples provided in the CO.28 Correlative Studies Manual. 6. Whole blood (that is not for ctDNA testing) will only be collected prior to enrollment. 7. Not required for patients that had a TME. 8. To be obtained within 28 days as close to the time of relapse as possible. Blood for correlatives done within 28 days PRIOR to date of relapse does not need to be repeated. 9. For CT pelvis and chest, a CT scan with contrast is preferred but not mandated. Patients with contrast allergies may undergo chest X-ray and /or Chest MRI. 10. Contrast is REQUIRED for the CT scan of the abdomen. Patients with contrast allergies may undergo liver ultrasound and /or MRI. 11. Rectal exam and proctoscopy are ideally to be performed by the primary surgeon. Proctoscopy should be performed ≤ 90 days prior to enrollment. Ideally, the surgeon should perform pre and post induction treatment proctoscopies. A gastroenterologist may perform proctoscopy in lieu of the surgeon, but then must also perform the follow-up exam. Proctoscopy may be accomplished using rigid proctoscopy or as part of a flexible sigmoidoscopy or colonoscopy. 12. For patients that had a TME it is only required at month 36. 13. If a rectal tumour tissue biopsy was performed within 90 days prior to enrollment, a repeat biopsy is not necessary. It is recommended that surgeons take a biopsy of the tumour during sigmoidoscopy/colonoscopy to ensure tissue availability and adequate pathology report confirming invasive well-moderately differentiated rectal adenocarcinoma and no evidence of pathologic high risk factors. 14. It is strongly encouraged that suspicious or unequivocal evidence of first local relapse be confirmed definitively by either biopsy (preferred) or by repeat/confirmatory imaging. Where imaging evidence of first local relapse is, in the opinion of the investigator and radiologist, absolutely unequivocal and not requiring subsequent confirmation by either biopsy or follow-up imaging, this must be clearly indicated in supporting documentation. 15. Urine pregnancy test in women of childbearing potential and if a false-positive is suspected this may include an ultrasound to rule-out pregnancy. 16. To be completed daily for patients receiving Capecitabine. 17. Adverse Events to be evaluated using the NCI Common Terminology Criteria for Adverse Events (CTCAE v5.0) (see Appendix III). 18. Only protocol chemotherapy or surgery related adverse events have to be reported after the 30 days post-excision visit. 19. After 3 cycles of FOLFOX or after 2 cycles of CAPOX.									

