7.3.3 Baseline Exams

- Sigmoidoscopy/colonoscopy: normal, abnormal non-malignant, abnormal malignant (**Table 7**)
- Other radiology investigations: normal, abnormal non-malignant, abnormal malignant (**Table 7**)
- Hematology: Hemoglobin, WBC, absolute neutrophil count (ANC), neutrophils, platelets, lymphocytes, basophils, monocytes, eosinophils (**Table 8**)
- Biochemistry: serum creatinine, total bilirubin, ALT, creatinine clearance (**Table 9**)
- Coagulation: PT, INR, PTT (**Table 10**)
- Baseline symptom status (**Table 11**)

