Kaplan-Meier method (**Figure 2**) will be used to estimate the 3 year loco-regional relapse rate and associated 95% confidence interval first among all patients treated with FOLFOX or CAPOX and TEMS or TAMIS (**Table 31**) and additionally among all patients that have received neoadjuvant chemotherapy.

7.7.3 3 Year Distant Relapse Rate

Distant relapse is defined as appearance of rectal cancer disease at sites remote from the rectum. The number of patients with each site of distant relapse (Lung, Liver, Brain, Distant lymph nodes, Bone, Skin, Ascites, Pleural effusion, Adrenal glands, Other) will be summarized (**Table 31**).

Distant relapse free survival is calculated as time from complete tumour surgical excision date (with pathology results negative for malignant disease within 1 mm of surgical margins) to the first date of definitive evidence (clinical, radiological or pathological) of distant relapses. Patients died, loss to follow up, or alive at clinical cut-off will be censored at respectively date of death, date of lost to follow-up, and last disease assessment date calculated as the last of dates of attendance/last contact on CRD Follow-up Report.

Kaplan-Meier method (**Figure 3**) will be used to estimate the 3 year distant relapse rate and associated 95% confidence interval first among all patients treated with FOLFOX

or CAPOX and TEMS or TAMIS (**Table 31**) and additionally among all patients that have received neoadjuvant chemotherapy.

7.7.4 3 year Disease Free Survival

Disease-Free Survival (DFS) is defined as the interval from complete tumour surgical excision date (with pathology results negative for malignant disease within 1 mm of surgical margins) to date of first occurrence of the events in the below.

- Locoregional relapse reported in CRF Relapse Report
- Distant disease reported in CRF Relapse Report
- Non-protocol radiotherapy, chemotherapy, or biologic therapy without documentation of the site of failure and reported in CRF Chemotherapy Report, Pre-Excision Report, and Surgery Report
- Death due to any other reason reported in CRF Death Report

Patients who are alive without locoregional or distant relapse or receiving non-protocol radiotherapy, chemotherapy, or biologic therapy without documentation of the site of failure at the analysis data cutoff date will be censored at their last disease assessment date calculated as the last of dates of attendance/last contact on Follow-up Report.

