7.8.5 Other safety

7.8.5.1 *Sigmoidoscopy/colonoscopy*

- Sigmoidoscopy/colonoscopy during protocol treatment (reported on CRF Chemotherapy Report, CRF Pre-Excision Report, and CRF Surgery Report): all normal, at least one abnormal but all non-malignant, all abnormal and malignant (**Table 43**)
- Sigmoidoscopy/colonoscopy during follow-up (reported on CRF Follow Up all normal, at least one abnormal but all non-malignant, all abnormal and malignant (**Table 43**)

7.8.5.2 *Other radiologic investigations*

- Other radiologic investigations during protocol treatment (reported on CRF Chemotherapy Report, CRF Pre-Excision Report, and CRF Surgery Report): all normal, at least one abnormal but all non-malignant, all abnormal and malignant (**Table 43**)
- Other radiologic investigations during follow-up (reported on CRF Follow-up REPORT): all normal, at least one abnormal but all non-malignant, all abnormal and malignant (**Table 43**)

7.8.5.3 *Transfusions*

- Number of patients who received any blood transfusions (red blood cells, platelets, and/or other) during protocol treatment (reported on CRF Chemotherapy Report, CRF Pre-Excision Report, and CRF Surgery Report) (**Table 44**)
- Number of patients who received any blood transfusions (red blood cells, platelets, and/or other) during follow-up (reported on CRF Follow-Up Report) (**Table 44**)

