	Red cell concentrates	**
	Platelets	**
	Other	**
Patients with Intraoperative injury	Site of Injury	** (**)
	Bladder	**
	Ureter	**
	Vein	**
	Artery	**
	Large bowel	**
	Small bowel	**
	Nerve injury	**
	Other	**
Hospitalization	Any time in intensive care	
	No	** (**)
	Yes	** (**)
	Days in intensive care	
	N	**
	Median	**
	Min-max	**_**
	Ongoing hospitalization	
	Yes	** (**)
	No	** (**)
	Days from admission for tumor excision to discharge	
	N	**
	Median	**
	Min-Max	**_**
	Discharge destination	
	Home	** (**)
	Assisted living (non-medical)	** (**)
	Skilled nursing home	** (**)
	Hospice	** (**)
	Chronic care hospital	** (**)
	Rehabilitation facility	** (**)
	Died	** (**)
	Transfer to other hospital	** (**)
	Other	** (**)

Table 40: All Deaths

Data set: All Chemotherapy Treated Patients		Number of Patients (%)
		N=**
		** (**)
Number of Patients who died		
Cause of Death		
Study-specific malignant disease only		**
Adverse event possibly, probably or definitely related to protocol treatment		**
Complication from a non-protocol treatment for this malignancy		**
Other primary malignancy		**
Other condition or circumstance		**

Table 41: Deaths Before Surgery

Data set: All Chemotherapy Treated Patients		Number of Patients (%)
		N=**
		** (**)
Number of Patients who died before surgery		
Cause of Death		
Study-specific malignant disease only		**
Adverse event possibly, probably or definitely related to protocol treatment		**
Complication from a non-protocol treatment for this malignancy		**
Other primary malignancy		**
Other condition or circumstance		**

Table 42: Adverse Event leading to Discontinuation of Neoadjuvant Chemotherapy

Data set: All Chemotherapy Treated Patients		Number of patients (%)
		N=**
Number discontinued neoadjuvant chemotherapy from adverse events		** (**)
<Adverse event 1> ^(a)		**
<Adverse event 2>		**
....		

(a): one patient may have more than one adverse event

Table 43: Sigmoidoscopy/Colonoscopy and Other Radiology Investigations

Data set: All Chemotherapy Treated Patients		Number of Patients (%)
		N=**
Sigmoidoscopy/colonoscopy during protocol treatment		
All Normal		** (**)
At least one abnormal but all non-malignant		** (**)
All Abnormal and malignant		** (**)
Sigmoidoscopy/colonoscopy during follow-up		
All Normal		** (**)
At least one Abnormal but all non-malignant		** (**)
All Abnormal and malignant		** (**)
Other Radiology investigations during protocol treatment		
All Normal		** (**)

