At least one abnormal but all non-malignant		** (**)
All Abnormal and malignant		** (**)
Other Radiology investigations during follow-up		
All Normal		** (**)
At least one abnormal but all non-malignant		** (**)
All Abnormal and malignant		** (**)

Table 44: Transfusion

Data set: All Chemotherapy Treated Patients		Number of patients (%)
		N=**
Number (%) of patients transfused during protocol treatment		** (**)
Type of transfusion		
Number of patients received Red Blood Cells		**
Number of patients received Platelets		**
Number of patients received Other Transfusions		**
Number (%) of patients transfused during follow-up		** (**)
Type of transfusion		
Number of patients received Red Blood Cells		**
Number of patients received Platelets		**
Number of patients received Other Transfusions		**

Table 45: Major Medical Problems

Data set: All Chemotherapy Treated Patients		Number of patients (%)
		N = ***
Any major medical problem during protocol treatment		
No		** (**)
Yes		** (**)
Type of medical problem during protocol treatment*		
Medical problem A		** (**)
...		** (**)
Any major medical problem during follow-up		
No		** (**)
Yes		** (**)
Type of major medical problem during follow-up*		
Medical Problem A		** (**)
...		** (**)

* one patient may have more than one medical problem

Table 46: Concomitant Medication

Data set: All Chemotherapy Treated Patients		Number of patients (%)
		N = ***
Any concomitant medication during protocol treatment		
No		** (**)
Yes		** (**)
Type of concomitant medications during protocol treatment*		
Medication A		** (**)
...		** (**)
Any concomitant medication 30 days after excision		
No		** (**)
Yes		** (**)
Type of concomitant medications 30 days after excision *		
Medication A		** (**)
...		** (**)

* one patient may have more than one medication.

Table 47: Anti-Cancer Treatment

Data set: All Chemotherapy Treated Patients		Number of patients (%)
		N = ***
Number of patients with any other anti-cancer treatment during protocol treatment		** (**)
Chemotherapy ⁽¹⁾		** (**)
Drug 1 ...		** (**)
Radiotherapy ⁽¹⁾		** (**)
Hormonal therapy ⁽¹⁾		** (**)
Drug 1 ...		** (**)
Immunotherapy ⁽¹⁾		** (**)
Drug 1 ...		** (**)
Other ⁽¹⁾		** (**)
Drug 1 ...		** (**)
Number of patients with any anti-cancer treatment during follow-up but before relapse		** (**)
Chemotherapy ⁽¹⁾		** (**)
Drug 1 ...		** (**)
Radiotherapy ⁽¹⁾		** (**)
Hormonal therapy ⁽¹⁾		** (**)
Drug 1 ...		** (**)
Immunotherapy ⁽¹⁾		** (**)
Drug 1 ...		** (**)

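### The three endoscopy and imaging categories in SAP Table 43 leave no row for a patient with both a malignant and a non-malignant result in the same period

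*SAP*

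**What the plan says.** A single examination has three possible results. SAP 7.3.3 gives them for baseline as "Sigmoidoscopy/colonoscopy: normal, abnormal non-malignant, abnormal malignant", and SAP 7.5.2 uses the same three for the pre-excision visit.

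SAP 7.8.5.1 (endoscopy) and 7.8.5.2 (other radiology) then reduce all of a patient's examinations in a period to one of three categories: "all normal, at least one abnormal but all non-malignant, all abnormal and malignant". The periods are protocol treatment and follow-up. For radiology in follow-up the text reads: "Other radiologic investigations during follow-up (reported on CRF Follow-up REPORT): all normal, at least one abnormal but all non-malignant, all abnormal and malignant". The endoscopy wording is the same.

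The Table 43 shell has four blocks (two types of examination, two periods). In each, the second row is "At least one abnormal but all non-malignant" and the third is "All Abnormal and malignant". No block has a mixed, other or not-done row. The data set is all chemotherapy-treated patients.

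The Protocol Section 5.0 flowsheet marks endoscopy in the post-excision column headed "Months 6, 12, 18, 24, 30 and 36". A footnote to it says: "For patients that had a TME it is only required at month 36".

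**The concern.** The third category requires every examination in the period to be malignant. On surveillance, a malignant finding will often come after one or more clear examinations. That patient is not all normal, not all non-malignant and not all malignant, so no row applies.

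Patients with only normal or benign results are always counted. Among patients with several examinations, those with a malignant result are counted only if every result was malignant. The error therefore runs one way, towards too few patients with a malignant finding. A programmer must either leave the others out or invent a rule that the SAP does not contain. SAP 7.1 warns that percentages may miss 100% through rounding, so a small shortfall could pass unnoticed.

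**Working it through.** The plan states no figure on this point, so there is none to reproduce. The check is whether the categories cover every possible set of results.

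**Inputs**
- Results per examination: normal (N), abnormal non-malignant (B), abnormal malignant (M) (SAP 7.3.3 and 7.5.2).
- Categories: the three in SAP 7.8.5.1, 7.8.5.2 and Table 43.
- Number of examinations in a period, k: from Protocol Section 5.0.

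**Step 1. Count patterns with no row, as worded.** There are 3^k ordered patterns. The 2^k without an M all fall in row one or row two. Of those with an M, only the all-M pattern has a row. Unclassified = 3^k − 2^k − 1.

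**Step 2. Repeat with a lenient reading.** Suppose row three means that every abnormal result is malignant, with normal results allowed. N then M now fits. Any pattern with both a B and an M still does not. Unclassified = 3^k − 2·2^k + 1.

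**Step 3. Repeat with row three as at least one M.** Every pattern has an M (row three), or a B but no M (row two), or only N (row one). Unclassified = 0, and no pattern falls in two rows.

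| k | Patterns | No row, as worded | No row, lenient | No row, reworded |
|---|---|---|---|---|
| 1 | 3 | 3 − 2 − 1 = 0 | 3 − 4 + 1 = 0 | 0 |
| 2 | 9 | 9 − 4 − 1 = 4 | 9 − 8 + 1 = 2 | 0 |
| 3 | 27 | 27 − 8 − 1 = 18 | 27 − 16 + 1 = 12 | 0 |
| 6 | 729 | 729 − 64 − 1 = 664 | 729 − 128 + 1 = 602 | 0 |

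At k = 6, 729 − 64 = 665 patterns contain a malignant result, and as worded only one of them has a row. These are counts of possible patterns, not probabilities. They show that the gap exists, not how many patients fall into it.

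**Step 4. Find where k reaches 2.**
- Follow-up endoscopy: up to six scheduled visits. After total mesorectal excision (TME) only month 36 is required, so this block mainly concerns patients without TME.
- Follow-up radiology: MRI at months 6, 18 and 30 (not required after TME) and CT at months 12, 24 and 36. The CT rows carry no TME exemption, so patients who had TME can be affected here.
- Protocol treatment: one endoscopy and one pelvic MRI are scheduled, both at the pre-excision visit. At k = 1 the categories are complete, so the gap opens only if further examinations are done.

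**Step 5. Trace where relapse is counted.** SAP 7.7.4 takes DFS relapse events from the Relapse Report ("Locoregional relapse reported in CRF Relapse Report", and likewise for distant disease). SAP 7.7.2 and 7.7.3 define the relapse times by dated evidence of relapse. All three feed Table 31. None uses the Table 43 categories, and neither does the organ preservation rate in SAP 7.7.1.

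**The case against.** The strongest reply is that nothing of consequence depends on Table 43. No endpoint, test or decision uses it, and relapses are tabulated by site in Table 31 with 3-year estimates. That stands. A reader might infer that malignant findings in follow-up disappear from the trial's results; the documents do not support this.

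A second reply is that the examination that detects relapse may never reach Table 43. Its follow-up blocks draw on the Follow-Up Report alone. The Protocol flowsheet has a separate first-relapse column with its own endoscopy, MRI and CT. Protocol Appendix III has a separate Relapse Report, and SAP 7.9 uses the Follow-Up Report for treatment before relapse. The case report forms are not in the documents. If the malignant examination is entered only on the Relapse Report, the patient is classified by the earlier examinations, and rewording row three would not recover the finding. This also stands, and it means the table cannot be said to miss exactly the patients who relapse.

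A reader might also want a patient count, obtained by applying the 8% and 18% local relapse rates in Protocol Section 2.0 to the trial. The 8% is for T1 tumours after local excision alone, and the 18% for T2 tumours after excision with chemoradiation; neither group had this trial's neoadjuvant chemotherapy. Locoregional relapse also includes pelvic disease that endoscopy need not show. The documents give planned sizes of 22, 50 and 58 but not the number of patients with two or more examinations in a period. Such a count is unsupported.

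None of these replies closes the gap in the categories. The lenient reading narrows it but leaves the patient with one benign and one malignant result without a row.

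**Conclusion.** The categories are wrong as written. They are not exhaustive once a patient has two or more examinations in a period, and every pattern left out contains a malignant result. Table 43 therefore understates patients with a malignant finding, to the extent that the malignant examination is recorded on the forms that feed it.

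The practical effect lies mainly in the two follow-up blocks. The number of patients cannot be derived: it depends on which form holds the malignant examination and on how many examinations each patient has had by the database lock. The primary endpoint, the 3-year relapse rates and DFS are unaffected. This is a minor correction to a descriptive safety table, and the conclusion rests on the wording alone, not on any assumed relapse rate.

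**What to change.** In SAP 7.8.5.1, 7.8.5.2 and all four blocks of Table 43, change the third category to *at least one abnormal and malignant*. The three categories are then mutually exclusive and cover every patient with at least one examination.

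The rewording alone will not make the percentages reach 100%, because the denominator is all chemotherapy-treated patients and those not examined in a period still have no row. Either base each block's percentages on patients with at least one examination in that period, or add a not-done row.

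The cost is an edit to the SAP text and the table shell. It needs no new data and no protocol amendment, and it changes no inference. While making it, the trial team could check whether the examination that detects relapse is entered on the Follow-Up Report, since that determines whether Table 43 can show it at all.

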7.8.5.4 Major medical problems

- Number of patients with each type of medical problems during protocol treatment (reported on Chemotherapy Report, CRF Pre-Excision Report, and CRF Surgery Report) (**Table 45**)
- Number of patients with each type of medical problems during follow-up (reported on CRF Follow-Up Report) (**Table 45**)

